4. To determine the extent of variation in measles antibodies in women of child bearing age in a population with a long standing measles vaccination program
5. To determine the extent of variation in rubella antibodies in women of child bearing age in a population where rubella vaccine have been recently introduced
6. To determine if variation in antibody levels in infants at 6 months is predominately explained by variation in starting antibody levels in the mother in this population
7. To estimate the half-life of decay of measles and rubella antibodies in infants

Methods:

This study will be an open-label, randomized, 2-arm clinical trial in healthy infants in Bangladesh. 620 children will be enrolled and randomized at 6 months of age to one of two study arms. The study design and participant evaluations are illustrated in Table.

Table: Schematic representation of study arms

Arm		Age of participant				
		6 months	9 months	11 months	Sample size	Enrollment target (sample size + 10% attrition)
A	MR 6 & 9 months	MR •	MR •	•	279	310
B	MR 9 months	•	MR •	•	279	310
Total (infants)					558	620
	Mothers	•			558	620

• Indicates blood collection
MR- Measles -rubella vaccination

Outcome measures/variables:

The primary end-point assessment will be based on **measles antibody titers (mIU/ml) (measured by the multiplex bead assay (MBA))** and rubella titers (IU/mL) (measured by ELISA) on sera collected 8 weeks after completion of vaccination series (at 11 months of age). Immune response is defined at 8 weeks after completion of vaccination series, as seropositivity post-vaccination if pre-vaccination antibody was undetectable (i.e. seroconversion), or a 4-fold or greater increase in antibody titers among pre-vaccination seropositives after adjusting for decline in maternal antibodies. Seroprotection is defined as antibody level of ≥ 120 mIU/mL for measles and >10 IU/mL for rubella. We will calculate the proportion of children attaining post-vaccination protective levels of antibodies.

Description of the Research Project

Hypothesis to be tested

Does this research proposal involve testing of hypothesis: No Yes (describe below)

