1. The study physician will complete the study questionnaire and examine the participant
2. 1 ml of blood will be drawn from each infant (both study arms A and B).
3. Study vaccine will be administered to ALL infants (both study arm A and B). The participant will be observed for 30 minutes to monitor for any adverse reactions
4. Schedule the next visit at 11 months of age

MR vaccination at 9 months is now routinely given in Bangladesh. Therefore, there will be no follow-up household safety monitoring visit after the 9 month MR dose during the study.

Temporary exclusion

- Participants who meet temporary exclusion criteria for vaccination will be excused for the day and will be requested to return several days later, but as long as their age is 9 months, +/- 7 days. A note will be made in the study log book.

Study site visit at 11 months of age. Blood draw and Study exit.

This visit will be the third and last planned study visit for participants. During this visit, the following procedures will be conducted:

1. The study physician will complete the follow up form and examine the participant
2. 1 ml of blood will be drawn from each infant (from both study arms A and B).
3. At study exit, parents will be reminded to bring their child to the fixed site clinic or another EPI facility to receive their second dose of measles vaccine according to the new EPI schedule (at age 15 months).

Laboratory evaluations

Clinical Laboratory Evaluations

No clinical laboratory evaluations will be offered in this study. Laboratory assays described in the protocol are for research purposes only and laboratory results will not be used for clinical diagnosis.

Special Assays or Procedures

Blood samples will be obtained at 6 months from all infants (at enrolment) and mothers and tested for measles and rubella antibodies. The baseline levels will identify infants who have transplacentally transferred maternal antibodies been exposed to natural measles infection before the enrolment to the study. The mothers' antibody levels will be determined and they will be classified as "susceptible" or "protected" (seroprotection definitions will be the same: titer of ≥ 120 mIU/mL for measles and rubella >10 mIU/mL).

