Multiplex bead assay detects antibodies against viral proteins in the serum of individuals who have been exposed to measles or rubella either by vaccination or natural infection. The MBA works by reading the fluorescent intensity of antigen-specific antibodies in serum binding to antigen coated beads and converting to antibody concentration using a standard curve. This is a novel IgG test for measles and rubella used at research labs. It is not commercially available and requires a significant amount of preparatory work to run the test and is not yet used to diagnose or confirm recent infection (IgM). Developing this capacity is not required for routine measles and rubella surveillance which the Bangladesh National Lab performs. Moreover, icddr,b has no prior experience in running MBA tests.

Measles and Rubella MBA testing will be conducted by the Measles, Mumps, Rubella, and Herpesvirus Laboratory at CDC, a WHO reference laboratory for measles virus. These tests will be performed as described by Smits et al.(31) The analytical cut-off value in the measles MBA assay is 153 mIU/ml. The concentration of antibody \geq 153 mIU/ml will be considered to be protective for measles. The analytical cut-off value in the rubella MBA assay is 9.36 IU/ml. The concentration of antibody \geq 9.36 IU/ml will be considered to be protective for rubella. There may be a formal comparison of rubella IgG concentrations between MBA and the standard EIA results.

Following testing of the samples by MBA, 5%-10% of the samples will also be tested by PRN for quality control testing.

Additional information regarding this assay is included in a detailed protocol maintained at the study laboratory.

Serum Measles IgG Antibody Detected by ELISA

Measles IgG testing will also be conducted by the Measles, Mumps, Rubella, and Herpesvirus Laboratory at CDC.

A commercial enzyme-linked immunosorbent assay (ELISA) will be used for the qualitative detection of IgG antibodies to Measles virus in human serum (Zeus Scientific Inc). Antigen specific antibody in the serum specimen binds to immobilized antigen and is complexed with an antibody linked to an enzyme. The color intensity of the solution depends upon the antibody concentration in the original test sample.

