Measles PRNT will be conducted by the Measles, Mumps, Rubella, and Herpesvirus Laboratory at CDC, a WHO reference laboratory for measles virus. PRNT will be performed as described by Cohen et al.(32) Assays will be standardized using WHO 2nd International Standard for measles antibody containing 5000 mIU/mL, which enables the 50% neutralizing antibody end-point dose (titer, ND50) of test samples to be transformed to antibody concentrations in terms of mIU/mL. The analytical cut-off value in this assay is ND50 < 1/8; this is the lowest dilution at which sera are tested. The interpretive cut-off value is ≥ 120 mIU/mL; this is the concentration of antibody considered to be protective. The term seroconversion will be used to refer to subjects whose SNA antibody levels changed from less than the interpretive cut-off value of 120 mIU/mL to equal or greater than the interpretive cut-off value of 120 mIU/mL.

Additional information regarding this assay is included in a detailed protocol maintained at the study laboratory.

Serum Rubella IgG Antibody Detected by ELISA

Rubella testing will also be conducted by the Measles, Mumps, Rubella, and Herpesvirus Laboratory at CDC, a WHO reference laboratory for rubella virus using a commercially available ELISA kit. For this test serial dilutions will be prepared at the CDC laboratory for the testing. The Zeus ELISA Rubella IgG test kit will be used to test for IgG class antibodies to Rubella virus in samples. In this assay, purified virus antigen is adsorbed onto a solid phase and the subject's serum is added. Any virus-specific antibody binds to the antigen, and virus-specific IgG is detected using anti-human IgG. The binding of virus-specific IgG is measured using a chromogen substrate. The colour intensity of the solution depends upon the antibody concentration in the original test sample. With this assay, a positive Index Standard Ratio (or optical density ratio) ≥ 1.10 (when converted to IU/mL, corresponds to ≥ 10 IU/mL) is positive for IgG antibody to rubella virus, and is considered protective for rubella.(33)

Additional information regarding this assay is included in a detailed protocol maintained at the study laboratory.

Specimen collection, handling and testing

Following universal precautions, 1 ml of blood will be collected from participants by venepuncture into a vacutainer at enrolment and at scheduled time-points during follow-up before administration of vaccine.

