Immune response is defined as a 4-fold increase in antibody titers 12 weeks after vaccination (post-6-month visit) compared with 6-month pre-vaccine titers accounting for the expected decline in maternal antibody titers or a change from antibody-negative to positive (i.e. seroconversion). In addition, quantitative data on antibody titers will allow us to assess the magnitude of seroresponse show as $-N$ -fold increases of pre- and post-vaccine titers. Seroprotection is defined as titer of ≥ 120 mIU/mL for measles and rubella >10 IU/mL

Secondary outcomes:

Several secondary outcomes will be assessed:

- 1) Secondary outcome is based on measles titers by MBA (mIU/ml) and rubella titers (IU/mL) by ELISA on sera collected 8 weeks after MR 9-month dose of vaccination (i.e., at 11 months) – post two dose series for participants in Arm A and 1 dose for arm B.
- 2) The safety profile of MR vaccine will be assessed by incidence of specific symptoms/problems. They will be categorized into one of the following three categories:
 - a) Immediate reactions (with emphasis on allergic reactions), occurring in the first 30 minutes post vaccination observed by study staff at the fixed site clinic.
 - b) Adverse events (AE) following 6-month MR dose that may occur during the 48 hours after 6-month MR vaccine administration. AEs will be graded and subcategorized as those deemed related to vaccination or not by the investigator.
 - c) Serious adverse events (SAEs) occurring from vaccination during the course of the study, identified or observed by study staff and/or reported by parent at any time during the study period. SAEs will be subcategorized as those deemed related to vaccination or not by the investigator and reviewed by the local Data and Safety Monitoring Board (DSMB) and icddr,b ERC committee.

Data Analysis

This is an open-label trial clinical trial that compares immunogenicity of MR vaccine schedules. The study will recruit 620 participants in 2 arms. Participants will be enrolled at 6 months of age and followed at 9 months and 11 months of age for a total of 5 months of follow-up.

General analytical issues

The data will be analysed by study investigators that include epidemiologists and statisticians. Statistical packages that would be used for the analysis include R, SAS and STATA.

The immunogenicity of each MR vaccination schedule will be determined by measuring antibody levels:

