- Blood samples will be obtained before each MR dose given (at 6 and 9 months) and at 11 months (i.e. 2 months after the last MR dose given at 9 months).
- Immune response is defined as a 4-fold increase in antibody titers 12 weeks after vaccination (post-6-month visit) compared with 6-month pre-vaccine titers accounting for the expected decline in maternal antibody titers or a change from antibody-negative to positive (i.e. seroconversion).
- The antibody titers (if present and detectable) at 6 months of age will be the starting point for the expected decline in maternal antibody.

- Laboratory quantitative data (i.e., titers) will allow seroconversion defined by other -fold increases to also be assessed. Seroprotection is defined as titer of ≥ 120 mIU/mL for measles and rubella >10 IU/mL.

We will assume that antibodies detected at 6 months are maternally-derived as no measles outbreaks have been detected in the area for the last few years; the number of reported measles cases has steadily declined since 2012 in Bangladesh (34) and Bangladesh conducted a nationwide MR campaign in 2013.

If the measles and rubella antibody titers are present and detectable at 6 months of age (at time of enrolment), these titers will be considered as the baseline IgG level for the expected decline in maternal antibody.

The rate of decay of maternal measles and rubella antibodies will be calculated for infants in study arm B based on change of measles and rubella antibody titers between 6 months and 9 months of age. This decay rate of measles and rubella antibodies will be incorporated in an analytical model when measuring post-6-month MR vaccine dose antibody response in infants in Study Arm A, and we will assess the impact of the maternal measles and rubella antibodies to immunogenicity of a 9-month MR vaccine dose. Seroprotection for measles is defined as concentration of ≥ 120 mIU/mL and rubella >10 IU/mL.

Possible limitations:

Taking into account that baseline measles or rubella antibodies detected at 6 months will be assumed as maternal antibodies, this may possibly lead to overestimation of the MR seroconversion rate. In some infants, measles or rubella antibodies may have developed in response to natural infection. It is impossible to determine with laboratory methods whether baseline measles or rubella antibodies are maternal or developed post-infection.

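### The rule that classifies mothers gives the rubella threshold in mIU/mL, 1000-fold below the IU/mL definition it says it repeats

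*Combined protocol and SAP*

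**What the plan says.** The rule for classifying mothers stands in one place, Special Assays or Procedures under Laboratory evaluations. It assigns each mother to one of two classes, susceptible or protected, and states that "seroprotection definitions will be the same". It then gives 120 mIU/mL as the measles cut-off and continues "for measles and rubella >10 mIU/mL".

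The other rubella thresholds are these:

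- Project Summary, Outcome measures/variables: ">10 IU/mL for rubella".
- Outcome measures/variables in the sample size section: "Seroprotection is defined as titer of ≥ 120 mIU/mL for measles and rubella >10 IU/mL".
- Data Analysis, General analytical issues: the same definition twice, the second time as "Seroprotection for measles is defined as concentration of ≥ 120 mIU/mL and rubella >10 IU/mL".
- Serum Rubella IgG Antibody Detected by ELISA: an index ratio of at least 1.10 "corresponds to ≥ 10 IU/mL" and is treated as protective.
- Primary analytical approach: children count as rubella seropositive at ≥10 IU/mL.
- Multiplex Bead Assay section: "The analytical cut-off value in the rubella MBA assay is 9.36 IU/ml", and concentrations at or above it are treated as protective.

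Secondary objective 3 asks for the proportions of mothers with undetectable, detectable and protective antibody, for measles and for rubella.

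**The concern.** The sentence contradicts itself. It announces a definition already in use and then prints a different one, with the measles unit attached to the rubella number. This is operative methods text, and it is the only statement of the maternal rule, so a programmer deriving the maternal variable would look there. Coded as printed, the cut-off lies far below the positivity limit of either rubella assay. The maternal rubella result under secondary objective 3 would then no longer separate mothers with some antibody from mothers with a protective level.

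**Working it through.** **Inputs.** The printed maternal threshold is 10 mIU/mL (Special Assays or Procedures). The comparison values are 10 IU/mL (outcome, analysis and ELISA sections) and 9.36 IU/mL (MBA section). The conversion is 1 IU = 1000 mIU.

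**Conversion.** 10 mIU/mL ÷ 1000 = 0.01 IU/mL.

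| Place | Rubella threshold | Ratio to 0.01 IU/mL |
|---|---|---|
| Special Assays or Procedures (mothers) | >0.01 IU/mL as printed | 1 |
| Outcome measures/variables (both places); General analytical issues (twice) | >10 IU/mL | 10 ÷ 0.01 = 1000 |
| Rubella ELISA; Primary analytical approach | ≥10 IU/mL | 1000 |
| MBA | ≥9.36 IU/mL | 9.36 ÷ 0.01 = 936 |

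The maternal rule is the only one in mIU/mL.

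**Effect on the classification.** The documents give no maternal rubella distribution, so this step is an illustration under an assumption. Suppose concentrations are log-normal with geometric mean GM and standard deviation s on the log10 scale, and all values are reported as numbers. The share above a cut-off c is 1 − Φ((log10 c − log10 GM)/s). The range tried is GM from 1 to 100 IU/mL and s from 0.4 to 0.8.

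| GM (IU/mL) | s | Share above 10 IU/mL | Share above 0.01 IU/mL |
|---|---|---|---|
| 1 | 0.4 | (1 − 0)/0.4 = 2.5, so 0.6% | 100.0% |
| 1 | 0.8 | (1 − 0)/0.8 = 1.25, so 10.6% | (−2 − 0)/0.8 = −2.5, so 99.4% |
| 20 | 0.6 | 69.2% | 100.0% |
| 100 | 0.4 | (1 − 2)/0.4 = −2.5, so 99.4% | 100.0% |

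Across the range, the share above 10 IU/mL runs from about 1% to 99%. The share above 0.01 IU/mL never falls below 99.4%. Under these assumptions the printed rule gives nearly the same answer whatever the true distribution.

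**Dependence on reporting.** In both assay sections the positivity cut-off is also the protective level. A detectable-but-not-protective group can therefore exist only if concentrations below that cut-off are reported as numbers. If they are, the printed threshold moves those above 0.01 IU/mL into the protected class. If they are reported only as negative or zero, those mothers stay susceptible under either unit and the slip changes little or nothing. The documents do not say which applies.

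**Reach.** Up to 620 mothers are classified. The sample size rests on an assumed 50% seroconversion after the 6-month dose and on 75% versus 65% after the 9-month dose. No maternal rubella value enters it.

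**The case against.** The strongest reply is that the sentence shows its own intent. It says it is repeating a definition, and that definition is given four times as >10 IU/mL and supported by both assay sections. An analyst using 0.01 IU/mL would have to override all of these, so the error may be caught without comment. The affected result is also a descriptive secondary proportion. Research assay results are not used for diagnosis, and field collection is described as complete, so trial conduct cannot change.

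Most of this stands. It supports reading the figure as a slip and not as a second, deliberately lower threshold, and it limits the consequence. It does not make the text correct: the only rule written for mothers still contradicts the definition it cites.

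Two stronger readings are tempting and are not supported:

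- A reader might infer that virtually every mother would be classed as protected. That needs a maternal distribution and a rule for reporting results below the cut-off, and the documents give neither.
- A reader might infer that the analyses of infant response by mother's antibody are corrupted as well. The list of analyses relates infant response to the mother's level of antibody. It does not say that the two-class split is used.

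**Conclusion.** The contradiction is certain and the factor of 1000 is exact. Applied literally, the rule counts any mother with a quantified rubella result above 0.01 IU/mL as protected, so the detectable and protective categories of secondary objective 3 effectively merge for rubella. The number of mothers who would change class is unknown, between almost none and almost all, depending on how results below the cut-off are reported and on the maternal distribution. The range in the table is an illustration and not an estimate for this population.

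Only the rubella part of secondary objective 3 is clearly affected. The unit slip leaves the infant primary endpoint, the comparison of arms and the sample size untouched. The correction is worth making because it is free and because this is the only place that states the maternal rule.

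**What to change.** 1. In Special Assays or Procedures, change the rubella unit for mothers from mIU/mL to IU/mL.
2. State once, for mothers and infants together, which assay, cut-off and inequality define protection, and replace the other statements with a cross-reference.
   - Rubella: the choice is between ELISA at ≥10 IU/mL and MBA at ≥9.36 IU/mL. The endpoint text names ELISA for rubella, but no section names the assay used to classify mothers. The choice between >10 and ≥10 matters only for a value of exactly 10.
   - Measles: the 120 mIU/mL in the maternal, outcome and analysis sections must be reconciled with the 153 mIU/mL that the MBA section calls protective, since MBA is the named measles assay. The two differ by a factor of 153 ÷ 120 = 1.275. This is separate from the unit slip and also bears on infant seroprotection.
3. Say how rubella results below the cut-off are reported, and what separates undetectable from detectable, so that the three categories of secondary objective 3 can be derived.
4. In Primary analytical approach, delete the stray '1:' before 120 mIU/mL, which mixes a dilution with a concentration. This is clerical.

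The cost is wording only: no new samples, no retesting for the unit correction and no change to the sample size. The change should be dated and made before the maternal results are classified.

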Infants acquire passive immunity to measles and rubella by transplacental transfer of maternal antibodies. (7, 8) These antibodies offer some protection for infants prior to receipt of MR vaccine. Mothers who have had natural infection in the past typically have higher titers of antibodies compared with women who have vaccine-induced antibodies and because of their lower titer, vaccine-derived maternal antibodies transferred to the infant decline to an undetectable level sooner than naturally-derived maternal antibodies. This has been documented by researchers who tested paired mother and infant serum samples for measles and rubella antibodies [1, 2] (some studies included blood samples drawn at week 36 of pregnancy and cord blood sample) [3, 4]. They reported that infants of vaccinated women have significantly lower antibody concentrations than did infants of naturally immune women, and infants of vaccinated women lose protective levels of antibodies sooner (i.e., by 6-8 months) than infants of naturally immune women [4].

A study in Matlab, Bangladesh(22) reported that in 1993, 67% of infants by age 5 months and 95% of infants by age 8 months had measles antibody titers below the threshold for protection leaving them susceptible to natural infection. As a result, a rising trend of measles cases below the eligible age of first routine measles vaccination, typically 9 or 12 months of age, has been observed. From 2004-2006, in Bangladesh an increase in the proportion of measles cases among infants <9 months of age was noted in

6 selected outbreaks. In these outbreaks 54% of cases were 6-8 months of age. From 2002-2009, 10% of confirmed measles cases in WHO African Region occurred among infants <9 months of age(23). In China, measles cases have been noted to have a bimodal distribution with majority of the cases either in adults up to age 30 in infants younger than 8 months, the routine age of first dose of measles vaccine. To improve the accuracy of interpretation of study results it would be prudent to test mothers of enrolled infants for measles and rubella antibodies. This will also enable us to determine the proportion of mothers with undetectable, detectable and protective levels of antibodies, and to assess the relationship between the level of antibodies in mothers and their infants' maternal antibodies.

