For participants in the study group A, the immune response to the 6 month MR dose will be measured at 9 months (blood drawn during the second visit) to evaluate both the proportion seroconverting (from negative to protected), 4-fold or greater increase in antibody titers among pre-vaccination seropositives, after adjusting for decline in maternal antibodies, as well as the magnitude of the immune response (expressed as geometric mean titers of the antibody response). The rate of decay of maternal measles and rubella antibodies will be calculated in infants in arm B based on the difference of antibody levels measured at 6 months (baseline) and 9 months. We will incorporate the model of maternal measles and rubella decay for infants in arm A to measure post-vaccine antibody levels and impact of the maternal

antibody to immune response in infants who had measles or rubella antibodies at enrolment. In the recently published study from Bangladesh, baseline measles virus serum neutralizing antibody seroprotection and anti-rubella virus IgG seroprotection at 9 months of age was low (0.42-1.25% and 0-0.42%, respectively) (21). If during this study, we determine that most children have no detectable levels of maternal measles or rubella antibodies at 6 months it would be impossible to calculate the decay. In this case, we will refer to antibody decay rates reported elsewhere (29, 30).

THE FOLLOWING CHANGES ARE MADE TO THE PROTOCOL:

Since the inception of the project and completion of the field data collection a newer assay, multiplex bead assay (MBA) for measles and rubella has been developed. It has been validated by the CDC measles and rubella laboratories.

Multiplex Bead Assay (MBA) for Serum Antibody Detection of Measles and Rubella

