- Collection of blood from mothers at time of enrolment to assess measles and rubella titers, as only one blood sample will be collected. (To assess the proportion of mothers with undetectable, detectable and protective levels of measles and rubella antibodies)
- Time from randomization to 9 and 11 months (To assess the correlation between measles and rubella antibody levels in women and levels of maternal antibodies in infants)
- Time from randomization to 9 months, Arm B (To estimate the half-life of decay of maternal measles and rubella antibodies in infants)

The primary end-point assessment is based on measles titers by MBA (mIU/ml) and rubella titers (IU/mL) by ELISA on sera collected 12 weeks after the first dose (time between 6 and 9 months) and 8 weeks after completion of vaccination (time between 9 and 11 months). Immune response is defined as a 4-fold increase in antibody titers 12 weeks after vaccination (post-6-month visit) compared with 6-month pre-vaccine titers accounting for the expected decline in maternal antibody titers or a change from antibody-negative to positive (i.e. seroconversion). However, quantitative data (i.e., determining titers) will allow seroconversion defined by other -fold increases to also be assessed.

We will calculate the rate of decay for those infants that have maternal antibodies detected at enrolment (at 6 months) in arm B (anti-measles or anti-rubella IgG levels at 6 months vs 9 months). We will incorporate the model of maternal decay for infants in arm A to measure post-vaccine antibody levels and impact of the maternal antibody to immune response. However, if we determine that most children have no detectable levels of maternal measles or rubella antibodies at 6 months it would be impossible to calculate the decay rate (in Arm B). In this scenario, we will refer to antibody decay rates reported elsewhere (29, 30).

Outcome measures/variables:

The primary end-point assessment is based on measles titers by MBA (mIU/ml) and rubella titers (IU/mL) by ELISA on sera collected 12 weeks after MR 6-month dose of vaccination (i.e., at 9 months) for study Arm A.

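### Maternal antibody decay in Arm B is taken from a 6-to-9-month difference with no rule for values below the assay limit, and the fallback can discard usable control data

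*Combined protocol and SAP*

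**What the plan says.** The single combined document describes the decay calculation in three places.

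- Special Assays or Procedures computes the Arm B rate "based on the difference of antibody levels measured at 6 months (baseline) and 9 months".
- General analytical issues repeats this as a rate "based on change of measles and rubella antibody titers between 6 months and 9 months of age", which is then carried into Arm A's response to the 6-month dose.
- Time to endpoint restricts the infants used: "We will calculate the rate of decay for those infants that have maternal antibodies detected at enrolment (at 6 months) in arm B".

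The fallback appears in the first and third of these sections: "if we determine that most children have no detectable levels of maternal measles or rubella antibodies at 6 months it would be impossible" to calculate decay, and rates reported elsewhere are then used.

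On how low the titres may be, Passive immunity reports for Matlab in 1993 that "67% of infants by age 5 months and 95% of infants by age 8 months had measles antibody titers below the threshold for protection". Special Assays or Procedures says that seroprotection for measles and rubella in an earlier Bangladesh study "at 9 months of age was low (0.42-1.25% and 0-0.42%, respectively").

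On the assay, the MBA section states "The analytical cut-off value in the measles MBA assay is 153 mIU/ml" and "The analytical cut-off value in the rubella MBA assay is 9.36 IU/ml", and treats each value as the protective level. It gives no lower limit of quantification. No section gives a scale, a fitted model or a rule for values below the limit, although decay is assumed to run at a fixed rate (Potential risks to participants).

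**The concern.** A difference between two titres is well defined only when both are quantified. Where the 9-month titre lies below the assay limit, the analyst must substitute a number or drop the infant. Substituting the limit understates the fall. Dropping the infant keeps the slow decliners. Both lengthen the estimated half-life.

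Two results depend on this rate. One is secondary objective 7, the half-life itself. The other is the immune-response definition, in which infants seropositive before vaccination must show a 4-fold rise after allowing for maternal decline. Too long a half-life sets too high an expected 9-month titre, so some true responders in Arm A would be counted as failures.

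The fallback looks at the wrong quantity. Whether decay can be estimated depends on how many infants are detectable at 6 months and how many of those are still quantifiable at 9 months. It does not depend on whether the detectable infants form a majority. When the rule fires, concurrent randomised control data are replaced by rates from other populations.

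**Working it through.** **Plan's own figure.** The documents state no sample size or precision for the decay rate. The only relevant number is 279 evaluable infants per arm (Sample size).

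**Step 1: expected titres.** Inputs from Passive immunity are 67% below the threshold at 5 months and 95% below at 8 months. Assume log-normal titres, log10 SD 0.5, and a threshold of 153 mIU/ml.

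- z(0.95) − z(0.67) = 1.645 − 0.440 = 1.205 SD over 3 months, or 0.402 SD per month.
- At 6 months: z = 0.440 + 0.402 = 0.842, so 20.0% are above 153.
- At 9 months: z = 0.440 + 4 × 0.402 ≈ 2.046, so 2.0% are above 153.
- Half-life = log10(2) / (0.402 × 0.5) = 0.301 / 0.201 = 1.50 months, about 46 days. It is 57 days at SD 0.4 and 38 days at SD 0.6.

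The 9-month figures in Special Assays or Procedures are lower still. For measles, 0.42% to 1.25% of 279 is 1.2 to 3.5 infants. For rubella, 0 to 0.42% is 0 to 1.2 infants.

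**Step 2: when the fallback fires.** For an assay limit L, the share detectable at 6 months is P(Z > 0.842 + log10(L/153)/0.5). It falls to 50% at L = 153 × 10^(−0.842 × 0.5) ≈ 58 mIU/ml (70 at SD 0.4; 48 at SD 0.6). Above that limit the fallback fires; below it the difference is used.

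**Step 3: half-life by estimator.** These are simulations of 279 Arm B infants with 30% CV in decay, assay SD 0.1 log10 and a true half-life of 46 days. The limits 51 and 19 are assumed values (153/3 and about 153/8). Results are median days.

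| Limit (mIU/ml) | Above limit at 6 mo | Above limit at 9 mo | Under the plan | Limit substituted | Non-detects dropped | Half limit substituted | Censored (Tobit) |
|---|---|---|---|---|---|---|---|
| 153 | 20% | 2% | fallback | not used | not used | not used | 44 |
| 51 | 54% | 14% | difference | 80 | 57 | 49 | 44 |
| 19 | 83% | 41% | difference | 62 | 52 | 46 | 44 |

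At 153, assay noise raises the expected number detectable from 0.20 × 279 = 56 to about 57. The Tobit estimate has a 5th-95th percentile range of about 34 to 53 days.

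**Step 4: a second model.** This one took 20% above the cut-off at 6 months and 1.25% at 9 months, SD 1 natural-log unit and within-infant correlation 0.9. The true half-life was 45 days.

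- Limit at the cut-off: the censored likelihood gave 43 days.
- Limit at a quarter of the cut-off, where the fallback would not fire: 72 days with the limit substituted, 50 from detectable pairs, 46 with half the limit, and 45 from the censored likelihood.
- Only 0.42% above the cut-off at 9 months: the censored median stayed close to the truth (37 against 35 days), but the spread across runs was very wide.

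**Step 5: effect on the 4-fold rule.** Over 91 days the expected fall is 2^(91/half-life), so the required 9-month titre is 4 / 2^(91/half-life) times the 6-month titre.

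- 46 days: 4 / 3.94 = 1.0
- 53 days: 4 / 3.29 = 1.2
- 80 days: 4 / 2.20 = 1.8

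**The case against.** **153 is not shown to be the censoring point.** The MBA reads concentration from a standard curve, assay detail sits in a laboratory protocol, and secondary objective 3 separates detectable from protective levels in mothers. That implies reportable values below protection. The 95% and 0.42-1.25% figures are shares relative to protection in other studies, and the latter is by neutralisation for measles. This stands. A reader might infer that nearly all 9-month titres will be censored, but the documents support that only as a forecast.

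**The two problems exclude each other.** At a limit of 153, substituting the limit gives a simulated half-life of about 106 days, and a reader might infer that the plan would report it. It would not: in that scenario about 80% are undetectable at 6 months, so the fallback replaces the difference. This also stands.

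**The plan names no substitution rule and does speak of a model.** It mentions a decay model and a fixed rate, and one cited fallback source has censoring in its title. With half the limit substituted, the bias at the lower limits is small (49 or 46 days). This stands in part. The error ranges from negligible to large according to a choice that the plan leaves open, and nothing in the trial's own analysis text mentions censoring.

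**Rubella may be beyond rescue.** If the limit is near the rubella cut-off, no Arm B infant may be quantifiable at 9 months, and a censored model then has no finite estimate. This stands, and published rates may be needed.

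**Conclusion.** The point holds, with medium confidence. The stated method has no rule for low 9-month values, and the stated trigger is tied to a majority rather than to whether decay can be estimated. The consequences for measles are alternatives:

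- **Limit near 153 mIU/ml:** the fallback discards about 57 usable infants.
- **Lower limit, 51 or 19 mIU/ml:** the difference is used, and the half-life can be anywhere from about right to 80 days against a truth of 46, depending on an unstated choice.

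The sizes rest on log-normal titres, the SDs and CV given above, and a Matlab threshold taken as 153. They do not extend to rubella.

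A reader might also infer that the primary comparison is badly distorted. The documents do not support that. Only infants seropositive at baseline are exposed to the decay adjustment (about 20% above threshold on this calibration), and no number of misclassified responders can be derived.

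**What to change.** Change Special Assays or Procedures, Time to endpoint and General analytical issues as follows.

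1. Estimate Arm B decay on the log scale with a left-censored (Tobit or mixed) regression in infants detectable at 6 months. State each assay's quantification limit in the plan and use it as the censoring point.
2. Replace the majority trigger, separately for measles and rubella. Use the trial's own rate if the censored model is adequately precise, which needs enough infants detectable at 6 months and some quantifiable at 9 months. State the precision required.
3. Use published rates when that condition fails, which is likely for rubella if its limit is near the cut-off. Otherwise use them as a sensitivity analysis.
4. Keep infants with rising titres in the main model, because removing them selects on the outcome and speeds up the estimated decay. Examine the exclusion of clear rises (for example 4-fold) only as a sensitivity analysis.

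The cost is a few lines of text and standard routines in R, SAS or STATA, with no new samples. The small downside is reliance on a log-normal assumption. The rule should be fixed before the titres are analysed.
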